# 4.3.3 Manufacturers recommended use will be adhered to:

- Before starting therapy, evaluate the patient's nutritional status and address severe malnutrition.
- Signs of possible infection or complications must be addressed immediately.
   Monitor the device, wound, surrounding skin, and patient status accordingly to ensure effective and safe treatment and patient comfort.
- For patients with ischemic condition or at application of a circumferential dressing, extra monitoring of wound status is required to avoid risk of compromised circulation.

- Avance Solo Pump is equipped with visual and audible notifications and alarms. Ensure that carrying or placement of the pump allows the user to detect audible and visual notifications and alarms.
- When Avance Solo Pump battery low alarm is triggered, replace the batteries in the pump. Only use the type and model of lithium batteries specified for this product by Mölnlycke Health Care, see section 8.
- Fixation strips provided with the dressing shall only be applied on dressing borders. Do not apply fixation strips, or other occlusive dressings, across the dressing wound pad due to the risk of low breathability leading to maceration.
- Application of certain skin protection products or using cleansing products prior to the application of the dressing, can affect the ability of the dressing and fixation strips to adhere securely and create sufficient sealing.
- Do not use the products on patient and/or user with known hypersensitivity to the ingoing materials/components of the products.
- Ingrowth of tissue may occur if the dressing or wound filler is not changed in accordance with recommendations or as appropriate for the wound condition of the individual patient (See Section 6.6).
- Consider use of non-adherent wound contact layer (Mepitel) to protect fragile tissue.
- Do not place the pump with canister in water or other liquids. Disconnect the pump and canister if the ingress of water is observed.
- For daily hygiene routines do not expose the pump with canister or dressing to extensive contact with water.
- Avance Solo Border Dressing should only be applied and changed by healthcare professional.
- No modification of this device (pump, canister, tubing, dressing, foam) is allowed as modifications may significantly compromise the ability of the system to deliver therapy.
- Do not disassemble the pump.
- Products in Avance Solo NPWT System should not be used with products from other NPWT systems.
- Do not cut the tubing or detach tubing from the canister.
- Do not cut the dressing.
- For CT scans and X-ray investigations, keep the pump out of the X-ray or scanner range. In the event that the pump is within a CT-scan or X-ray range, ensure to check that the pump functions correctly after the procedure.
- Avance Solo Pump is not intended for use aboard aircraft. Remove batteries during air travel.
- Avance Solo NPWT System products are provided sterile. Do not use if the sterile barrier is damaged or has been opened prior to use. Do not re-sterilize.
- Avance Solo Pump is for single patient use.
- Avance Solo Border Dressing, Avance Solo Foam and Avance Solo Canister 50 ml are single use.
- Do not reuse Avance Solo NPWT System products. If reused, performance of the product may deteriorate, cross contamination may occur.
- HAAMPOD will be placed via commercially available dressing instructions.

Ensure that the battery lid on the Avance Solo Pump is closed during therapy.

#### 4.4 WITHDRAWAL

Any patient who interrupts the evaluation treatment for longer than 3 days will be withdrawn from the evaluation.

Patients who do not respond to therapy should be withdrawn from the evaluation only at the point where it becomes necessary to change the treatment on clinical grounds.

Patients may drop out or be withdrawn for the following reasons:-

- at their own request\*
- at the discretion of the clinician (because of lack of response, an adverse incident, poor compliance etc.).
- as their incision is no longer suitable for treatment with Avance® Solo
- \* Although patients need not give a reason for requesting withdrawal from the evaluation, the Clinician should make a reasonable effort to ascertain the reason(s), while fully respecting the patient's rights.

Patients who drop out or who are withdrawn from the evaluation will not be replaced if they have been entered onto the study and have received evaluation treatments.

Patients who drop out or who are withdrawn or whose wound heals will not be reentered into the evaluation at a later date.

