# 1 INTRODUCTION

# 1.1 RATIONALE

To determine if "high risk" surgical incisions develop healing complications within 21 days of surgery. High risk is defined as a standard incision in the "high risk patient" (diabetes, obesity, poor anatomy, malnutrition). Or a "high risk incision" such as a foot and ankle incision, flap incision or major soft tissue resection with a large amount of dead space.

A healing complication is defined as the presence of at least one of these clinical scenarios: infection (superficial or deep), (evidenced by the prescription of oral antibiotics,(partial, superficial, or deep), or delayed healing (incision not 100% closed within 7 days of the first surgical procedure). Ongoing wound drainage from the incision after 96 hours, periwound erythema, minor dehiscence or major dehiscence.

The purpose of this study is to assess the efficacy of the FDA cleared device, Avance® Solo, an device that delivers negative pressure wound therapy to closed incisions (NPWTi), and to assess the number of healing complications that result from its use, compared to the current hospital standard Optifoam® Gentle Post op Dressing (a silicone backed foam that is conformable, with a border that is waterproof, flexible and breathable for increased comfort, with a wear time of up to seven days). This foam is currently stocked by the operating rooms at Mount Sinai hospital and indicated for use in high risk wounds (although there is no data to support its usage).

Historically, the use of negative pressure wound therapy for surgical incisions can assist in the management of surgical incisions. There are thought to be at least 6 positive mechanisms of action; protects the incision from the external environment, removes surface drainage and lymphatic drainage, resists gaping through application of lateral tension, increase breaking strength of healed incisions, reduces seroma and haematoma fluid collections, reduces edema, improves perfusion compared to area not treated with NPWT.

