# 1.2 OBJECTIVE(S)

The primary objective is to assess the frequency of a wound healing complication, in a closed incisional wound in a "high risk" surgical incision when treated with NPWTi versus a highly absorbent antimicrobial post – operative absorbent dressing. (HAAMPOD).

A healing complication is defined as presence of at least one of the following conditions: infection (superficial or deep), dehiscence (partial, superficial, or deep), or delayed healing (incision not 100% closed within 7 days of the first surgical procedure), drainage form the wound after 96 hours post operatively.

The secondary objectives are to assess any changes in the following assessments of the surgical incision weekly over the treatment period:

- Surrounding skin condition
- Incision complications, infection or clinical signs of infection
  - to assess the number and type of these complications individually including other postsurgical complications: skin necrosis, cellulitis, abscess, suture abscess, seroma, periwound edema or hematoma occurring within 21, 42, and 90 days postoperatively
- Pain during dressing changes

Assessment of the following at dressing changes:

- Duration/wear time
- Ease of use; difficulty with sleep
- Damage to surrounding skin on removal
- · Assessment of re-epithelialization/closure
- Patient comfort during wear; ease of ambulation
- Conformability of dressing
- Exudate management
- Reasons for removal

To assess the overall comparison of Avance® Solo to the HAMMPOD.

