#### 2 EVALUATION DESIGN

# 2.1 EVALUATION DESIGN

Open label, two armed, prospective, single center, quality equivalency assessment.

Immediate post operative application of Avance® Solo Negative pressure wound therapy on "high risk" closed surgical incisions. Versus the hospital best clinical practice dressing HAAMPOD. (Please note there is no prospective clinical data driven data, the hospital purchasing department develops and indicates the brand based upon cost).

The patient will be undergoing:

- Foot and ankle surgery
- Vascular groin incision, vascular axillary incisions
- Long leg vein harvest incision
- Closed forefoot and major amputation surgery
- Possibly: breast augmentation and reduction surgery

\*Note: The surgical indication is chosen based upon previously published data of high risk incisions. (It is beyond the scope of a protocol to educate the IRB in regards to the full definitions of high risk surgical inicisions)

Patients will participate in the study for 4 applications or up to 2 weeks treatment, whichever comes first. During this time clinicians will be asked to complete questions pertaining to the incision and to the performance and overall acceptability of Avance®Solo or the HAAMPOD.

Throughout the evaluation patients will be treated according to the product instructions for use for either product.

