# 4.3.2 Exclusion Criteria

- Incisions in excess of effective dressing pad size provided.
- Patients with a known history of poor compliance with medical treatment.
- Patients who have participated in this trial previously and who were withdrawn.
- Patients with known allergies to product components (silicone adhesives and polyurethane films (direct contact with incision), acrylic adhesives (direct contact with skin), polyethylene fabrics and super-absorbent powders (polyacrylates) (within the dressing).
- Incisions where daily inspection is required underneath the dressing.
- Incisions which have an infection which is not being treated with systemic antibiotics.
- Incisions which are actively bleeding.
- Exposure of blood vessels, organs, bone or tendon at the base of the reference incision.

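### Section 4.4 takes patients out of the evaluation for reasons that can relate to the outcome, and nothing in the plan keeps them in follow-up or in the comparison by randomised arm

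*Combined protocol and SAP*

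**What the plan says.** Section 4.4 (Withdrawal) makes one exit mandatory: "Any patient who interrupts the evaluation treatment for longer than 3 days will be withdrawn from the evaluation". Non-responders are withdrawn once treatment has to change on clinical grounds. Patients may also leave at their own request, or "at the discretion of the clinician (because of lack of response, an adverse incident, poor compliance etc". A further reason names only one of the two products: "as their incision is no longer suitable for treatment with Avance® Solo". On numbers, the section adds: "Patients who drop out or who are withdrawn from the evaluation will not be replaced", provided they had been entered and treated.

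The outcome window is longer than the treatment period. Section 1.1 asks whether high-risk "surgical incisions develop healing complications within 21 days of surgery". Section 1.2 extends the individual complications to those "occurring within 21, 42, and 90 days postoperatively". Section 5.2 schedules visits at days 21, 42 and 90. Treatment ends earlier, as section 2.1 states: "Patients will participate in the study for 4 applications or up to 2 weeks treatment, whichever comes first".

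Section 8 plans a chi-squared test of complication yes/no between two randomised groups. It defines no analysis population and gives no rule for patients whose outcome is unknown. Section 2.1 describes the trial as open label.

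**The concern.** The rule withdraws the patient from the evaluation, not merely from the dressing. Lack of response, an adverse incident or a necessary change of treatment can each be an early sign of the primary outcome: infection, dehiscence, delayed healing or continuing drainage. The clinician who decides knows the arm, and one reason is worded for Avance Solo only, so withdrawal may operate differently in the two arms.

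If withdrawal ends follow-up, patients at raised risk of a later complication could leave before it is seen, and at rates that differ by arm. Section 8 says the pilot is there to check the assumptions for a larger trial. The observed complication rates are therefore its main product, and they are what selective loss would distort. With so few expected events, one lost event is visible in the result.

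**Working it through.** **1. Does any section settle what happens after withdrawal?**

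| Place | Suggests follow-up ends | Suggests only the dressing phase ends |
|---|---|---|
| 4.4 | Withdrawal is from the evaluation | Non-replacement fits withdrawn patients still counting among the 30 per arm; patients whose wound heals are also barred from re-entry |
| 4.3.2 | Bars "Patients who have participated in this trial previously and who were withdrawn", so withdrawal is from the trial | – |
| 2.1 | – | Participation is described as at most two weeks |
| 5.2 | Its heading calls the later visits an evaluation | Visits are set for the patient in general, with no exclusion |
| 6.1, end of evaluation | Interruption over 3 days and withdrawal are reasons for ending | Wound closure is in the same list, and closed wounds presumably still attend later visits |

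The wording supports both readings, and no sentence chooses between them.

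**2. Could the outcome be captured another way?**

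- Section 6.1 records complications at each dressing removal, so events up to the last removal are captured.
- Section 7 reports only product-related adverse events. An ordinary late infection need not appear there.
- Section 10.4 allows data to be taken from the electronic medical record (EMR) but does not mention withdrawn patients.

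The exposure is therefore mainly the patient withdrawn early whose first complication comes later.

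**3. Inputs.** Section 4.1 gives 30 per arm. Section 8 gives expected rates of 16% (or 5/30) for control and 8% (or 2/30) for negative pressure therapy. I use the counts because they reproduce the plan's 162 per arm for a powered study. With two-sided alpha 0.05 (sidedness is my assumption), power 0.8 and mean rate 0.1167:

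n = [1.960 × √(2 × 0.1167 × 0.8833) + 0.842 × √(0.1667 × 0.8333 + 0.0667 × 0.9333)]² / 0.10² = 161 per arm.

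The rounded 16% and 8% give 258 per arm by the same formula. That mismatch is a separate matter.

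**4. Effect of one patient.**

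| Change | Control (5/30 = 16.7%) | Avance Solo (2/30 = 6.7%) |
|---|---|---|
| One event patient dropped | 4/29 = 13.8% (−2.9 points) | 1/29 = 3.4% (−3.2) |
| One event scored as no complication | 4/30 = 13.3% (−3.3) | 1/30 = 3.3% (−3.3) |
| One event-free patient dropped | 5/29 = 17.2% (+0.6) | 2/29 = 6.9% (+0.2) |

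Difference between arms when event patients are dropped:

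- none: 16.7 − 6.7 = 10.0 points
- one control event: 13.8 − 6.7 = 7.1
- one Avance Solo event: 16.7 − 3.4 = 13.2 (unrounded rates)
- one in each arm: 13.8 − 3.4 = 10.3 (unrounded rates)

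**5. How likely is a loss?** The documents give no rate. As an assumption, let each of the 5 + 2 = 7 expected event patients have an independent chance q of going uncounted.

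| q | Expected missed, 7q | At least one missed, 1 − (1 − q)⁷ | Three or more of the five control events missed |
|---|---|---|---|
| 5% | 0.35 | 30% | 0.1% |
| 10% | 0.70 | 52% | 0.9% |
| 20% | 1.40 | 79% | 5.8% |

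**6. Scale.** The exact (Clopper–Pearson) 95% interval is 5.6% to 34.7% for 5/30 and 0.8% to 22.1% for 2/30.

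**The case against.** The best reply is that withdrawal in section 4.4 refers only to the dressing phase. The section treats healed patients like withdrawn ones as regards re-entry, and section 6.1 lists wound closure as a reason for ending. If leaving the evaluation cancelled the later visits, every patient who healed under the dressing would be lost too, and those visits would have little purpose. This reading is reasonable, so the plan cannot be said to end follow-up for certain. But the plan does not state it, and two members of site staff could handle the same patient differently.

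Second, many outcome-related withdrawals would already count as events, because the composite is broad and complications are recorded at dressing removal. This stands. It narrows the problem to late first events and makes heavy one-arm losses unlikely.

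Third, a shift of about 3 points is small beside the exact intervals, and the data are declared exploratory. This also stands, and it limits the severity. However, an interval shows sampling error but not selective loss, and the loss is avoidable.

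Fourth, two randomised groups and a chi-squared test imply comparison as randomised. That is the natural reading, but it does not say what happens to a patient with no known outcome. The consent form, which I have not seen, may cover data use after withdrawal, but that would not replace a follow-up and analysis rule in the protocol.

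**Conclusion.** The concern holds. Section 4.4 removes patients from the evaluation for reasons that can relate to the outcome, and no section keeps them in the day 21, 42 and 90 assessments or in the comparison by randomised arm. Each uncounted event moves an arm's rate by about 3 points, roughly a third of the expected 10-point gap. Losing an event-free patient hardly matters.

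The sizes rest on the plan's own expected counts. The chances of a loss rest on assumed rates of 5% to 20%, independent between patients. The direction of any bias cannot be predicted. Since the study is an exploratory pilot, the harm is to the rates carried into the larger trial and not to a confirmatory conclusion. It should be fixed before data are collected, because outcomes that were never recorded may not be recoverable.

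**What to change.** Leave the clinical reasons for stopping a dressing as they are, and make these changes:

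- **Section 4.4:** state that stopping the study dressing does not end follow-up. Every randomised patient is followed to days 21, 42 and 90, by visit or by medical record where consent allows, unless consent is withdrawn.
- **Section 8:** state that the chi-squared comparison is by randomised arm and counts any protocol-defined complication recorded before or after stopping. Stopping alone is not an event.
- **Reporting:** give withdrawals and unknown outcomes by arm and reason. A best-case and worst-case analysis is optional.
- **Consistency:** the sponsor should reconcile the withdrawal reason that names only Avance Solo with the two-arm design.

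The cost is a few sentences. The visits are already scheduled, so the only burden is some extra visits, contact or record review for patients who would otherwise have left.

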# 5 TREATMENT PLAN

# 5.1 TREATMENT REGIME

Patients will be informed of the evaluation requirements and asked to give informed consent prior to any evaluation activities taking place.

Patients meeting the eligibility criteria and agreeing to consent to their participation in this evaluation will receive treatment with Avance® Solo for a maximum of 2 kits or up to a maximum of 2 weeks treatment, whichever comes first. If randomized to HAAMPOD the patient will have a dressing applied per manufacturers guidelines. Up to 4 dressings will be applied over 14 days. Treatment will commence on Day 0 and dressing changes will take place as deemed necessary by the evaluation Clinician.

Avance® Solo should be applied in accordance with standard protocols and the product instructions for use.

The following table details the treatment regime for participation patients in the study.

Pre-Trial	Investigator discusses evaluation with the patient
	and provides the patient with a centre consent form

		for use of their data and photographs.
		Patient provides informed consent Complete eligibility checklist and medical history
±	First Dressing Application (Day 0)	Incision assessment Incision photograph First dressing application Video recording may be carried out
weeks Treatment	Second Dressing Application	First dressing removal Incision assessment Incision photograph Second dressing application Video recording may be carried out
Maximum of 2 we	Third Dressing Application	Second dressing removal Incision assessment Incision photograph Third dressing application Video recording may be carried out
Maxi	Fourth Dressing Application	Third dressing removal Incision assessment Incision photograph Fourth dressing application Video recording may be carried out
	Post Study	A patient interview may be carried out

# At each dressing change the following will be assessed:

- Duration/wear time
- Ease of use;
- Difficulty with sleep
- Damage to surrounding skin on removal
- Assessment of re-epithelialization/closure
- Patient comfort during wear
- Ease of ambulation
- Conformability of dressing
- Exudate management
- Reasons for removal

# 5.2 FURTHER POST OPERATIVE EVALUATION

The patient will be seen on day 21 ( $\pm$ 3), 42 ( $\pm$  5) and 90 ( $\pm$  7) at all time points the wounds will be assessed for:

Healing complications, defined as presence of at least one of the following:

- infection (superficial or deep)
- dehiscence (partial, superficial, or deep)
- delayed healing (incision not 100% closed within 7 days of the first surgical procedure).
- Ongoing wound drainage > 7 days post operatively

Secondary objectives are to assess the number and type of these complications individually including:

- wound drainage, type and amount;
- wound margin and periwound areas;
- and other aspects including but not limited to odor, pain, and need for debridement.
- skin necrosis, incisional pain, cellulitis, abscess, suture abscess, or hematoma occurring within 21, 42, and 90 days postoperatively.

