#### **Precautions:**

The use of anticoagulants does not deem a patient inappropriate for treatment with the Avance® Solo, however, haemostasis must be achieved before applying the dressing and continued frequent assessment must be maintained and considered throughout the therapy.

Avance® Solo must not be placed over exposed arteries, veins or organs. Greater care should be taken with respect to weakened, irradiated or sutured blood vessels or organs.

Avance® Solo is contraindicated for patients with malignancy in the incision site or margins of the incision (except in palliative care to enhance quality of life), previously confirmed and untreated osteomyelitis, non-enteric and unexplored fistulaes, sinus tracts and areas of tunnelling or necrotic tissue with eschar or exposed anastomotic sites, use over exposed blood vessels, nerves or organs or use on exposed bone or tendon unless a non-adherent dressing is used to protect the exposed areas.

Avance® Solo is registered in the country of use (CE marked for Europe and 510k approved for the US).

A number of different dressing sizes are produced by the sponsor, Molnlycke (shown in Table 1).

Table 1: Molnlycke dressing sizes

Dress	ing size	Effective pad size	Pad Area (cm²)
Document Number:	1	Document Part:	000
Document Version:	01	Document Status:	Released

10cm x 20cm	5cm x 15cm	75
10cm x 30cm	5cm x 25cm	125
10cm x 35cm	5cm x 30cm	150
15cm x 15cm	10cm x 10cm	100
15cm x 20cm	10cm x 15cm	150
15cm x 30cm	10cm x 25cm	250
20cm x 20cm	15cm x 15cm	225
25cm x 25cm	20cm x 20cm	400

The dressing and pad sizes that will be used for the closed incision wounds in this study are listed below (shown in Table 2).

Table 2: Dressing sizes to be used in the study

Dressing size	Effective pad size	Pad Area (cm²)
10cm x 20cm	5cm x 15cm	75
10cm x 30cm	5cm x 25cm	125
10cm x 35cm	5cm x 30cm	150
15cm x 20 cm	10cm x 15cm	150
15cm x 30cm	10cm x 25cm	250

3.2 OPTIFOAM® GENTLE POST-OP – (MEDLINE IN, NORTHFIELD IL) – IS A "SILICONE FACED AND BORDERED POST OPERATIVE FOAM AND SUPERABSORBENT CORE AND FLEXIBLE DESIGN." (PER PACKAGE INSERT) THIS PRODUCT IS DEEMED ADEQUATE FOR HIGH RISK SURGICAL INCISIONS PER MOUNT SINAI VALUE ANALYSIS/ (NOT SUBJECT TO IRB APPROVAL NOR REVIEW)/PURCHASING. WHICH WILL BE KEPT IN PLACE FOR UP TO 7 DAYS (PER PACKAGE INSERT), ALTHOUGH DRESSING CHANGES UP TO 4 PER 14 DAYS WILL BE ALLOWED. \*NOTE THIS PRODUCT IS SUBJECT TO CHANGE BASED UPON MOUNT SINAI PURCHASING CONTRACTS.

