# At dressing removals the following information will be requested

- Dressing changed since last assessment (yes/no) (if yes how many times has the dressing been changed).
- Dressing in place (yes/no) obtain photograph
- Damage to surrounding skin (none, mild, moderate, severe)
- Level of damage to the reference wound on removal (none, slight, moderate, severe)
- Level of damage to the surrounding skin on removal (none, slight, moderate, severe)
- Condition of surrounding skin on removal (Healthy, fragile, inflamed, macerated, dry and flaky, other)
- Assess closure/ re epithelialisation of the incision
- Patient comfort during wear (Very comfortable, comfortable, acceptable, uncomfortable, very uncomfortable)
- Exudate level (None, slight, moderate, heavy)
- Assessment of infection (yes/no)
- Any incision complications and / or clinical signs of infection present (None, incision site static or deteriorating, dehiscence, increased exudate/secretion levels, increased pain, increased temperature around the wound, discolouration of granulation tissue, friable granulation, tissue necrosis, local erythema, oedema, purulent drainage, odour, other)
- Photographs (yes/no)
- Pain on removal of dressing (None, mild, moderate, severe)
- Reasons for removal (Dressing saturated, strike through, leakage, pain, Fell
  off, removed by patient, suture/staple removal, patients own request,
  inspection prior to patient discharge, other)
- Ease of use at this assessment (only at final removal)
- Occurrence of any product related adverse events will be documented at any point during the evaluation if required
- Is another dressing being applied at this assessment (yes / no?)

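### Seroma is a counted secondary outcome in section 1.2 but a prompted item on no assessment list, and haematoma has no prompted, dated entry during treatment

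*Combined protocol and SAP*

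**What the plan says.** Section 1.2 lists, as a secondary objective, the number and type of individual complications, including "skin necrosis, cellulitis, abscess, suture abscess, seroma, periwound edema or hematoma occurring within 21, 42, and 90 days postoperatively". The sentence that introduces the secondary objectives asks for "changes in the following assessments of the surgical incision weekly over the treatment period".

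Section 5.2 sets the follow-up visits at Day 21 (±3), Day 42 (±5) and Day 90 (±7). It restates the secondary objective for those visits, ending with "skin necrosis, incisional pain, cellulitis, abscess, suture abscess, or hematoma occurring within 21, 42, and 90 days postoperatively". The item just before that one is open-ended: "and other aspects including but not limited to odor, pain, and need for debridement".

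Section 6.1 gives an enumerated list of complications and signs of infection to be recorded at each dressing removal. It ends with "tissue necrosis, local erythema, oedema, purulent drainage, odour, other". Neither seroma nor haematoma is among its options.

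Under section 5.1, treatment lasts at most two weeks, with dressing changes when the clinician thinks them necessary. Section 2.1 describes the trial as open label.

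**The concern.** An objective that counts a complication needs a form that asks about it. If seroma is not a listed item, a blank cannot distinguish a seroma that was looked for and not found from one that nobody considered. Because the clinicians know the allocation, the readiness to volunteer an unprompted finding may also differ between arms.

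The item has some scientific weight here. Section 1.1 includes "reduces seroma and haematoma fluid collections, reduces edema" among the mechanisms thought to explain how negative pressure helps, and section 1 cites a small hip-arthroplasty study of seroma volume. A pilot that section 8 says is meant to validate basic assumptions would be expected to record collections in the same way in both arms.

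For haematoma the issue is narrower. It is on the Day 21 list, but no list used while the dressing is in place asks about it. An early haematoma would thus be dated and described from recall or from notes.

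**Working it through.** No sample-size, power or alpha figure is involved, and the plan states no figure to reproduce. The check compares lists and adds one calculation of timing.

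**Step 1: the objective against its restatement.** Section 1.2 names seven complications in the quoted item; section 5.2 names six.

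- In both: 5 (haematoma is one of them).
- In 1.2 only: 2 (seroma and periwound edema), and 5 + 2 = 7.
- In 5.2 only: 1 (incisional pain), and 5 + 1 = 6.

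**Step 2: every assessment list.**

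| List | Seroma | Haematoma | Oedema | Open entry for complications |
|---|---|---|---|---|
| 5.1, each dressing change | no | no | no | no |
| 5.2, Days 21, 42 and 90 | no | yes | no, but the periwound area is assessed | yes |
| 6.1, baseline | no | no | yes | yes |
| 6.1, dressing-change assessments | no | no | no | no |
| 6.1, dressing removals | no | no | yes | yes |
| 6.1, end of evaluation | no | no | no | no |

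Seroma is named on 0 of 6 lists and haematoma on 1 of 6. Oedema is named on 2 of 6, so periwound edema is lost only from the follow-up list.

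**Step 3: timing of the first prompt for haematoma.**

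- Last possible treatment day (section 5.1): Day 14.
- First visit whose list names haematoma (section 5.2): 21 − 3 = Day 18 to 21 + 3 = Day 24.
- Interval from the last possible treatment day: 18 − 14 = 4 days to 24 − 14 = 10 days.

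This interval separates the end of treatment from the first prompt. It is not a period excluded from the outcome: both 1.2 and 5.2 count complications from surgery, so a haematoma during treatment belongs in the Day 21 count.

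**Step 4: effect on the primary outcome.** The definitions of a healing complication in 1.1, 1.2 and 5.2 do not name seroma or haematoma. The primary composite does not depend on these items.

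**The case against.** The strongest reply is that the plan already has ways to capture these events. The dressing-removal checklist has an entry for anything else, and the follow-up list is expressly not exhaustive. Section 10.4 draws data from the electronic medical record, so a drained collection or a re-operation should leave a trace. Section 6.1 records freedom from re-admission. Section 7 takes product-related adverse events at any time. Section 9.1.1 refers to questionnaires created by the investigator team, which are not in the documents and may contain the missing items. The objective in 1.2 also stands even where 5.2 abbreviates it.

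Much of this is fair, and it limits the point to prompting and consistency. It does not remove it. An open entry allows a record but does not ask for one. The medical record is a partial backstop that depends on what was noted in routine care. Section 7 excludes events not judged product-related, and its device-effect clause covers only Avance Solo, so it gives no like-for-like comparison of the arms. The fix does not blind the clinicians either; it only ensures that the same question is asked of every patient.

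Three stronger readings are tempting, and the documents do not support them.

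- A reader might infer that bleeding is a named device risk left unmonitored. The text on anticoagulants says that "haemostasis must be achieved before applying the dressing and continued frequent assessment must be maintained and considered throughout the therapy". With the exclusion of actively bleeding incisions, that is a precaution for use. Bleeding is neither listed as a device risk nor set as an outcome.
- A reader might infer that no haematoma data would exist from the treatment period. The outcome window runs from surgery, so such events are due to be counted at Day 21. What is missing is a prompted, dated entry at the time.
- A reader might take collections to be the main reason for the device. Section 1.1 presents their reduction as one of at least six proposed mechanisms, and the largest study cited concerns deep infection and dehiscence.

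**Conclusion.** The point holds as a minor mismatch between a stated secondary objective and the lists meant to serve it. Seroma is prompted at no visit. Haematoma is prompted from Day 21 (Day 18 at the earliest) and retrospectively covers the treatment period. Periwound edema is missing only from the follow-up list and is largely covered during treatment by the oedema option.

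The size can be stated only as coverage: 0 of 6 lists for seroma, 1 of 6 for haematoma, and 4 to 10 days between the last possible treatment day and the first haematoma prompt. The documents give neither a seroma rate nor a rate of unprompted recording, so any estimate of missed events would be invention. Section 8 calls the data exploratory, so the comparison of these items would in any case be descriptive.

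The conclusion assumes that the forms follow the lists in 5.1, 5.2 and 6.1. If the questionnaires already ask about seroma and haematoma at each assessment, only the protocol text needs aligning.

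**What to change.** 1. In section 5.2, add seroma and periwound edema to the Day 21, 42 and 90 list so that it matches section 1.2.
2. In section 6.1, add seroma and haematoma to the dressing-removal checklist in both arms, each as yes/no with onset date and whether any drainage or re-operation took place.
3. State that each is reported descriptively by arm, counting events from Day 0.
4. Check that the questionnaires carry the same items.

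The cost is a few tick-boxes at assessments already planned and slightly longer forms. These are recording items only: no procedure, visit or clinical rule changes. The change should be made before data collection, because prompted and dated findings cannot be reliably rebuilt from notes afterwards.
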